10.8 HCV Resistance Analyses

For all subjects, full length NS3/4A and NS5A from baseline samples will be sequenced by next generation sequencing (NGS). For subjects who experience virologic failure (on-treatment virologic failure or post-treatment relapse as defined in Section 10.1), full length NS3/4A and NS5A from the first sample after virologic failure with HCV RNA ≥ 1000 IU/mL will be sequenced by NGS. Subjects treated with study drug who do not achieve SVR₁₂ due to reasons other than virologic failure (i.e., prematurely discontinued study drug with no on-treatment virologic failure, HCV reinfection, missing SVR₁₂ data or other reasons as described in Section 10.1, Reasons for SVR₁₂ Non-Response), but have a time point with HCV RNA ≥ 1000 IU/mL after treatment discontinuation, will have the sample at that time point sequenced.

Only samples with an HCV RNA level of ≥ 1000 IU/mL will undergo sequence analysis in order to allow accurate assessment of products of amplification. Therefore, if the HCV RNA level at the time of HCV virologic failure or treatment discontinuation is < 1000 IU/mL, the sample closest in time after HCV virologic failure/treatment discontinuation with an HCV RNA level ≥ 1000 IU/mL will be used.

For each DAA target, signature amino acid positions and a key subset of amino acid positions for the respective inhibitor class are listed in Table 9. Appropriate subtype-specific prototypic reference sequence will be used for comparison with sequences from samples.

Table 9. Signature Amino Acid Positions and the Key Subset of Amino Acid Positions

Target	Signature Amino Acid Positions	Key Subset of Amino Acid Positions
GT1 NS3	36, 43 (GT1a only), 54, 55, 56, 80, 107, 122, 132 (GT1a only), 155, 156, 158, 168, 170, 175 (GT1b only)	155, 156, 168 (all GTs)
GT2, 3, 4, 5, 6 NS3	36, 43, 54, 55, 56, 80, 155, 156, 166 (GT3-only), 168	
GT1 NS5A	24, 28, 29, 30, 31, 32, 54 (GT1b only), 58, 62, 92, 93	24, 28, 30, 31, 58, 92, 93 (all GTs)
GT2, 3, 4, 5, 6 NS5A	24, 28, 29, 30, 31, 32, 58, 92, 93	

Included time points for analyses on samples from subjects who do not achieve SVR₁₂ are 1) the sample closest in time after failure/discontinuation with an HCV RNA level of ≥ 1000 IU/mL, and 2) 12 weeks post-DAA treatment, provided that resistance-associated variants were detected by NGS at the time of HCV virologic failure/treatment discontinuation.

The following definitions will be used in the resistance analyses:

- Baseline polymorphism: a polymorphism by NGS in a baseline sample ($\geq 2\%$ or $\geq 15\%$ prevalence within a subject's viral population depending on polymorphism frequency threshold utilized) that was not present in the appropriate prototypic reference amino acid sequence for a given DAA target (NS3/4A or NS5A).
- Substitution at signature amino acid position: substitution (relative to reference) present at a detection threshold of $\geq 2\%$ or $\geq 15\%$ (depending on frequency threshold utilized) within a subject's viral population in a baseline or a post-baseline sample at a signature amino acid position.
- Post-baseline substitution: an amino acid substitution in a post-baseline time point sample that was not detected at baseline ($< 2\%$) in the subject and is detectable in $\geq 2\%$ of the sequences from the post-baseline sample.

- Enriched polymorphism: polymorphism present in both the baseline and a post-baseline sample whose prevalence in the post-baseline sample is at least 20 percentage points greater than the prevalence in the baseline sample [(post baseline % – baseline %) \geq 20].
- Treatment-emergent substitution: A post-baseline substitution or an enriched polymorphism.

Analysis 1: The following analyses will be provided for all subjects by HCV subtype,:

- By-subject listings of all baseline polymorphisms at signature amino acid positions for each DAA target (NS3/4A and NS5A) at detection thresholds of 2% and 15%.
- The number and percentage of subjects with baseline polymorphisms at signature amino acid positions at detection thresholds of 2% and 15%.
- Total number and percentage of subjects with baseline polymorphisms at a key subset of amino acid positions in NS3 only, in NS5A only, any in NS3, any in NS5A, any in NS3 or NS5A, any in NS3 + NS5A, by subtype, and total (include all subtypes).

Analysis 2: The impact of baseline polymorphisms on treatment outcome will be assessed as follows: for each polymorphism, the SVR₁₂ rate will be calculated for subjects with and without the polymorphism and the 2 rates will be compared. Analysis will be grouped by HCV subtype, and DAA target (NS3/4A or NS5A).

The following will be included in the analyses of impact of baseline polymorphisms on treatment outcome:

- For each signature amino acid position, presence of any polymorphism at that position (vs no polymorphism at that position), using detection thresholds of both 2% and 15%.
- Each individual polymorphism at each signature amino acid position (vs not that polymorphism) using detection thresholds of 2% and 15%.

Analysis 3: In subjects with or without polymorphisms in NS3 only, in NS5A only, any in NS3, any in NS5A, any in NS3 or NS5A, any in NS3 + NS5A at the key subset of amino acid positions at 15% detection threshold, the SVR₁₂ rate will be calculated, and the rates with or without polymorphisms will be compared using Fisher's exact test. Analysis will be separated by HCV subtype.

Analysis 4: The following analyses will be performed for subjects who do not achieve SVR₁₂, and who have post-baseline resistance data available:

- Listings by subject of all treatment-emergent substitutions relative to the baseline amino acid sequences will be provided for each DAA target (NS3/4A and NS5A).
- Listings by subject and time point of substitutions at signature amino acid positions (relative to reference sequence) will be provided for each DAA target (NS3/4A and NS5A).

HCV Genotype/Subtype

Phylogenetic analysis will be conducted on HCV NS3/4A and/or NS5A sequence from baseline samples from all subjects in order to accurately determine genotype/subtype. If the phylogenetic analysis is not available, then the result from Sanger sequencing of a region of NS5B by AbbVie or by the Central laboratory will be used to determine the subject's HCV genotype/subtype, if available. Finally, if neither the phylogenetic analysis result nor the Sanger sequencing assay results is available, then the Inno-LiPA assay results from the Central laboratory will be used to categorize the subject. This information will be presented in summaries of efficacy subgroup analyses.

The baseline characteristic summary will use the results from the central laboratory (Sanger sequencing or Inno-LiPA 2.0 Assay [if Sanger sequencing not available]). A summary of HCV genotype subtype as provided by the central laboratory (Sanger sequencing or Inno-LiPA 2.0 Assay [if Sanger sequencing not available]) versus

phylogenetic analysis also will be provided. Listing of HCV genotype and subtype will be provided separately for central laboratory results and phylogenetic analysis results.

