The presence of baseline polymorphisms in NS3 and/or NS5A did not have an impact on SVR₁₂ rates for GT1-, 2-, 4-, 5-, or 6-infected subjects.

Within GT3-infected subjects, baseline polymorphisms in NS3 did not have an impact on treatment outcome. The NS5A polymorphisms at positions 24, 28, 31, 58, 92, or 93 (including Y93H) did not have an impact on treatment outcome, whereas the A30K polymorphism was associated with a slightly decreased SVR₁₂ rate. Given the low prevalence of A30K (6.3%; 39/615) and that the majority of subjects with A30K achieved SVR₁₂, its impact on overall SVR is expected to be minimal.

Amino Acid Substitutions in Subjects Experiencing Virologic Failure

Among TN and TE-PRS subjects without cirrhosis or with compensated cirrhosis treated for 8, 12, or 16 weeks, 23 subjects experienced virologic failure (2 with GT1, 2 with GT2, and 19 with GT3). A GT3-infected subject experiencing virologic failure was determined to have been reinfected with GT3a virus distinct from the one present at baseline.

Therefore, baseline polymorphisms and treatment-emergent substitutions were analyzed for 22 subjects experiencing virologic failure.

Among the 2 GT1-infected subjects, 1 had treatment-emergent substitutions A156V in NS3 and Q30R/L31M/H58D in NS5A, and 1 had treatment-emergent Q30R/H58D (while Y93N was present at baseline and post-treatment) in NS5A.

Among the 2 GT2-infected subjects, no treatment-emergent substitutions were observed in NS3 or NS5A; the prevalent M31 polymorphism in NS5A was present at baseline and post-treatment in both subjects.

Among the 18 GT3-infected subjects, the majority of subjects had treatment-emergent substitutions at the time of failure in NS3 (61.1%, 11/18) and NS5A (88.9%, 16/18). Treatment emergent NS3 substitutions Y56H/N, Q80K/R, A156G, and Q168L/R were observed in 11 subjects, and A166S or Q168R was present at both baseline and post-treatment in 5 subjects. Treatment-emergent NS5A substitutions M28G, A30G/K, L31F, P58T, or Y93H were observed in 16 subjects, and 13 subjects had A30K (n = 9) or Y93H (n = 5) at both baseline and post-treatment.

Integrated Safety Results

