8.0 Statistical Methods and Determination of Sample Size

8.1 Statistical and Analytical Plans

An interim data lock may occur in the study if interim study results are needed for regulatory interaction purposes. No changes to the study design or treatment of subjects would result from this interim analysis; therefore, no adjustment for multiplicity is needed.

SAS® (SAS Institute, Inc., Cary, NC) for the UNIX operating system will be used for all analyses. All confidence intervals will be two-sided with an alpha level of 0.05.

Descriptive statistics will be provided, such as the number of observations (N), mean, and standard deviation (SD) for continuous variables and counts and percentages for discrete variables.

Safety and demographic analyses will be performed on all subjects who receive at least one dose of study drug.

Efficacy analyses will be performed on the intention-to-treat (ITT) population defined as all enrolled subjects who receive at least one dose of study drug, unless otherwise specified.

Sensitivity analyses of the primary efficacy endpoint, when applicable, will be performed on the intention-to-treat population modified to exclude subjects who did not achieve SVR₁₂ for reasons other than virologic failure (mITT-VF).

No data will be imputed for any efficacy or safety analysis except for analyses of SVR endpoints (HCV RNA data). HCV RNA values will be selected for the analyses of all SVR endpoints (e.g., SVR₄ and SVR₁₂) based on defined visit windows. A backward imputation method will be used to impute missing responses for SVR analyses.

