- Enriched polymorphism: polymorphism present in both the baseline and a post-baseline sample whose prevalence in the post-baseline sample is at least 20 percentage points greater than the prevalence in the baseline sample [(post-baseline % – baseline %) \geq 20].

- Treatment-emergent substitution by NGS: A post-baseline substitution or an enriched polymorphism detected by NGS.

Analysis 1: The following analyses will be provided for all subjects, separated by HCV subtype:

- By-subject listings of all baseline polymorphisms at signature amino acid positions for each DAA target (NS3/4A and NS5A) at detection thresholds of 2% and 15%.
- The number and percentage of subjects with baseline polymorphisms at signature amino acid positions at detection thresholds of 2% and 15%.
- Total number and percentage of subjects with baseline polymorphisms at a key subset of amino acid positions in NS3 only, in NS5A only, any in NS3, any in NS5A, any in NS3 or NS5A, any in NS3 + NS5A, by subtype, and total (include all subtypes).

Analysis 2: The impact of baseline polymorphisms on treatment outcome will be assessed as follows: for each polymorphism, the SVR₁₂ rate will be calculated for subjects with and without the polymorphism and the 2 rates will be compared. Analysis will be grouped by HCV subtype and DAA target (NS3/4A or NS5A).

The following will be included in the analyses of impact of baseline polymorphisms on treatment outcome:

- For each signature amino acid position, presence of any polymorphism at that position (vs no polymorphism at that position), using detection thresholds of both 2% and 15%.
- Each individual polymorphism at each signature amino acid position (vs not that polymorphism) using detection thresholds of 2% and 15%.

Analysis 3: In subjects with or without polymorphisms in NS3 only, in NS5A only, any in NS3, any in NS5A, any in NS3 or NS5A, any in NS3 + NS5A at the key subset of amino acid positions at 15% detection threshold, the SVR₁₂ rate will be calculated, and

the rates with or without polymorphisms will be compared using Fisher's exact test. Analysis will be separated by HCV subtype.

Analysis 4: The following analyses will be performed for subjects who do not achieve SVR₁₂ and who have post-baseline resistance data available:

- Listings by subject of all treatment-emergent substitutions relative to the baseline amino acid sequence will be provided for each DAA target (NS3/4A and NS5A).

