4.2 Design Diagram

[figure not shown]
This is a Phase 3b, open-label, multicenter study to evaluate the efficacy and safety of GLE/PIB for an 8- or 12-week treatment duration in adults in Brazil with chronic HCV GT1 – 6 infection, without cirrhosis or with compensated cirrhosis with a METAVIR System Fibrosis Score of F2, F3 or F4 (F2 - F4) or equivalent, who are HCV treatment-naïve. Approximately 100 subjects meeting the eligibility criteria will be enrolled. The study enrollment will be monitored to meet the following enrollment criteria: 1) a minimum of approximately 35 GT1 and 25 GT3 subjects and 2) approximately 80 F2 – 3 and a maximum of approximately 20 F4 subjects.

Subjects will be enrolled into one of the following treatment arms:

- Arm A: HCV GT 1 – 6 without cirrhosis (F2 – F3) subjects will be treated with GLE/PIB 300 mg/120 mg once daily (QD) for 8 weeks.
- Arm B: HCV GT 1 – 6 subjects with compensated cirrhosis (F4) will be treated with GLE/PIB 300 mg/120 mg once daily (QD) for 12 weeks.

A study schematic is shown below in [Figure 1](#).

Figure 1. Study Design

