4.3 Sample Size

It is anticipated that a total of approximately 100 HCV infected treatment naïve GT1 – 6 subjects will be enrolled in this study. No formal hypothesis is being tested. If

the observed SVR₁₂ rate in this study is 97% among 100 HCV GT1 – 6 treatment naive subjects, then the half-width of 2-sided 95% normal approximation to the binomial distribution confidence interval will be 3.3% (EAST 6.4).

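### Resistance Analysis 3 reports a per-subtype Fisher p-value with no interval for the SVR12 difference, so it usually cannot show how large a polymorphism effect remains possible

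*SAP*

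**What the plan says.** SAP 10.8, Analysis 3, calculates SVR12 by polymorphism status at the key amino acid positions (15% detection threshold), and "the rates with or without polymorphisms will be compared using Fisher's exact test. Analysis will be separated by HCV subtype". Protocol 8.1.4 has the same analysis; its groupings begin "In subjects with or without polymorphisms in NS3 only, in NS5A only, any in NS3, any in NS5A" and go on to the combined NS3 and NS5A categories.

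Three neighbouring provisions matter:

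- Analysis 1 tabulates the prevalence of polymorphisms "by subtype, and total (include all subtypes"). That total covers prevalence, not SVR12.
- Analysis 2 works per position and per polymorphism: "the SVR₁₂ rate will be calculated for subjects with and without the polymorphism and the 2 rates will be compared". It is also grouped by subtype and names no test or interval.
- The Wilson intervals in SAP 10.6 do not list polymorphism status among the subgroups.

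Protocol 8.1 states "All confidence intervals will be two-sided with an alpha level of 0.05". Neither document sets a level, or a rule for reading the p-value, for the Fisher test. SAP 10.2 rules out hypothesis testing for the primary and secondary endpoints only.

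**The concern.** The stated purpose of this group of analyses is to assess the impact of baseline polymorphisms on outcome. A study of about 100 subjects with SVR12 near 97% has few failures, and splitting it by subtype leaves fewer in each test. A large p-value is then the expected result with no effect, and a common one with a sizeable effect. A p-value alone does not tell the reader which differences the data exclude.

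What is at stake is the wording of the report. Protocol 3.0 says of the much larger integrated dataset "The presence of baseline polymorphisms in NS3 and/or NS5A did not have an impact on" SVR12 in genotypes 1, 2, 4, 5 and 6. A similar sentence in this report, resting only on p > 0.05 in 25 to 35 subjects, would have no support.

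**Working it through.** **The plan's own figure.** The only precision figure in the documents is the half-width for 97% of 100: 1.96 × √(0.97 × 0.03 / 100) = 0.0334, or 3.3%. It reproduces. Nothing comparable is given for Analysis 3.

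**Inputs from the documents**

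- Size (SAP 4.3): "a total of approximately 100 HCV infected treatment naïve GT1 – 6 subjects will be enrolled". Genotype targets (SAP 4.2): "a minimum of approximately 35 GT1 and 25 GT3 subjects". These are genotype sizes; no subtype sizes are given.
- Genotype mix in Brazil (Protocol 3.0): GT1 65%, GT3 30%, GT2 5%.
- NS5A carriers (Protocol 3.0): GT1 26.8%, GT3 22.1%, GT2 79.8%. NS3 carriers: GT1 1.1%, GT3 1.6%.
- Treatment-naive failures (Protocol Table 2): GT1 6/561 = 1.1%; GT2 4/369 = 1.1%; GT3 22/521 = 4.2%.

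**Assumptions.** A 20-point loss in carriers; a two-sided 0.05 level; GT1 split almost evenly into 1a (32) and 1b (33); GT3 treated as one subtype.

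**Smallest attainable p-value.** With no failures, p = 1. With one failure, the smallest two-sided p is the carrier fraction:

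- GT3, n = 25: 6/25 = 0.24
- GT3, n = 30: 7/30 = 0.233
- GT1a, n = 32: 9/32 = 0.281

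**Chance of 0 or 1 failure**, (1−f)ⁿ + n·f·(1−f)ⁿ⁻¹:

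- GT3, n = 25, f = 0.042: 0.342 + 0.375 = 0.717
- GT1a, n = 32, f = 0.011: 0.702 + 0.250 = 0.952

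**Power.** Let x of m₁ carriers and y of m₀ non-carriers fail, with failure probabilities f₁ and f₀. Power is the sum over all (x, y) of Bin(x; m₁, f₁) × Bin(y; m₀, f₀), counting only tables with two-sided Fisher p < 0.05.

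| Subtype (carriers vs non-carriers) | 10-point loss | 20-point loss | 30-point loss |
|---|---|---|---|
| GT3, 6 vs 19, f₀ = 4.2% | 3% | 13% | 29% |
| GT3, 7 vs 23, f₀ = 4.2% | 12% | 30% | 49% |
| GT1a, 9 vs 23, f₀ = 1.1% | 6% | 25% | 51% |

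The miss rate for 20 points is therefore 70 to 87%. The upper end is sensitive to one table. With 6 carriers in 25, two failures that are both carriers give p = 15/300, exactly 0.05; if that counted as significant, power in the first row would be 26%, not 13%.

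At the planning rate (97% vs 77%), with 26.8% carriers, the miss rate by subtype size is:

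| Subtype size | 12–23 | 25 | 30 | 35 | 40 | 45 | 50–55 |
|---|---|---|---|---|---|---|---|
| Missed | 87–94% | 86% | 76% | 70% | 67% | 63% | 49% |

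Sizes of 12 to 23 arise if the GT1 minimum of 35 is split into 1a and 1b.

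**NS3.** The chance of no carrier at all in a subtype is 0.984²⁵ = 0.67 for GT3 and 0.989³² = 0.70 for GT1a. The one-failure limit above does not apply here: a single carrier who fails among 35 gives p = 1/35 = 0.029. With one carrier, the miss rate is still 92% (n = 35) or 89% (n = 25) at 97% vs 77%.

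**What an interval adds.** Newcombe 95% limits, carriers minus non-carriers:

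- 5/6 vs 19/19: p = 0.24; difference −17 points, interval −56 to +5.
- 6/6 vs 19/19: p = 1.0; difference 0, interval −39 to +17.

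**A total row.** An exact test stratified by subtype on about 100 subjects has simulated power of about 80% (strata 35, 35, 25 and 5; 97% vs 77%) to 85% (strata 32, 33, 30 and 5; Table 2 failure rates) when every subtype has the 20-point loss. If the loss is confined to GT3, it has 25%, against 30% for the GT3 Fisher test alone (n = 30). At 30 points the figures are 42% and 49%.

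**The case against.** The strongest case against has four parts.

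**The benchmark effect is too large for most strata.** In Table 2, GT1 had 8 failures among 889 treatment-naive or previously treated subjects (TE-PRS). At 26.8% carriers, about 238 were carriers; even if all 8 failures were among them, carrier failure was at most 8/238 = 3.4%. For GT2 the bound is 6/(0.798 × 466) = 1.6%. This stands: a uniform 20-point loss is a benchmark, not an expectation. In GT3 the same bound is 31/(0.221 × 643) = 22%, so that dataset does not exclude a large loss there by this arithmetic.

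**Pooling can hide the signal.** Protocol 3.0 reports slightly lower SVR12 with the NS5A polymorphism A30K in GT3. An effect in one subtype is diluted in a combined test, as shown above. This stands, and it is why a stratified test should not become the main comparison.

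**Subtype separation is deliberate.** Reference sequences and signature positions are subtype-specific (SAP Table 9 distinguishes GT1a from GT1b). This stands; the per-subtype rows should stay.

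**The study is descriptive.** No formal hypothesis is tested, and Analysis 3 touches no primary or secondary endpoint. This limits the weight of the point. It also favours reporting an estimate with an interval over a p-value alone.

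**Conclusion.** The point holds as a reporting weakness in an exploratory analysis. The only named inferential output on polymorphisms and SVR12 is a p-value per subtype. For NS5A it usually cannot reach 0.05 at the documents' failure rates (72% and 95% in the two cases worked). It misses an assumed 20-point loss about 70 to 87% of the time at sizes of 25 to 35, and 49 to 94% at sizes from 12 to 55. These miss rates rest on the assumed effect and level, and on subtype sizes that the documents do not give.

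A reader might infer three stronger things that the documents do not support:

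- That polymorphism impact is judged only by p-values. The SVR12 rates are reported as well, and Analysis 2 compares rates descriptively.
- That the plan treats p > 0.05 as no impact. It sets no such rule. The Protocol 3.0 sentence excludes GT3, and the next paragraph reports the A30K decrease.
- That a non-significant result is nearly certain even when carriers do worse. Power is 13 to 30% for a 20-point loss and 29 to 51% for 30 points in the cases worked.

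**What to change.** In SAP 10.8, Analysis 3:

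1. For each comparison, report the SVR12 difference (carriers minus non-carriers) with a two-sided 95% score-based interval beside the Fisher p-value. Newcombe's method is built from Wilson limits and so matches the plan's other intervals.
2. State that any conclusion of no impact will rest on the interval limit, not on p > 0.05.
3. Keep the per-subtype rows as planned. A total row stratified by subtype may be added as a supplement, with a note that it dilutes an effect confined to one subtype.
4. State that the 10-subject minimum for intervals in SAP 10.6 does not apply here. Carrier groups of 6 to 9 would otherwise get none.

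Record the change in SAP 12.1, since Protocol 8.1.4 carries the same Analysis 3 text.

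The cost is one extra column and a sentence of wording, with no new data, visits or subjects. Intervals will be wide in small subtypes, which shows what the data leave open.

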Post-treatment relapse is defined as described earlier (**Relapse₁₂** and **Relapse_{overall}**), and no genotype, subtype, or clade switch compared with baseline as determined by phylogenetic analysis of the NS3 or NS5A gene sequences. If phylogenetic analysis is not possible due to technical difficulties, the subject will be defined as having a post-treatment relapse unless an HCV genotype or subtype switch is confirmed by the Versant HCV Genotype Inno-LiPA Assay v2.0 or Sanger assay.

Reasons for SVR₁₂ Non-Response

Subjects who do not achieve SVR₁₂ (SVR₁₂ non-responders) will be categorized as having:

1. On-treatment virologic failure (see **On-treatment virologic failure** definition);
2. HCV reinfection (see definition described earlier);
3. Relapse₁₂;
4. Prematurely discontinued study drug with no on-treatment virologic failure (defined as any SVR₁₂ non-responder who prematurely discontinued study drug [study drug duration < 52 days for Arm A and < 77 days for Arm B] and did not meet the **On-treatment virologic failure or reinfection** definitions);
5. Missing follow-up data in the SVR₁₂ window (defined as any subject who completed study drug without data in the SVR₁₂ window after applying the imputation rules and not meeting the definitions of [1], [2], [3], or [4]);

6. Other (defined as any SVR₁₂ non-responder not meeting the definitions of [1] – [5]).

For the reasons for SVR₁₂ nonresponse defined above, subjects are only to be counted in 1 category. Specifically, subjects who were SVR₁₂ nonresponders meeting the definition of HCV reinfection will be counted in the reinfection category regardless of whether they meet the definition of prematurely discontinued study drug or relapse₁₂.

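### SAP 10.8, Analysis 4: the treatment-emergent listing does not leave out reinfected subjects, so differences between two separate viruses would be listed as treatment-emergent

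*SAP*

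**What the plan says.** - **Who enters Analysis 4.** SAP 10.8: "Analysis 4: The following analyses will be performed for subjects who do not achieve SVR₁₂, and who have post-baseline resistance data available". No reason for non-response is excluded.
- **Reinfection counts as non-response.** SAP 10.1 puts reinfection second among six reasons for missing SVR12. A reinfected non-responder "will be counted in the reinfection category regardless of whether they meet the definition of prematurely discontinued study drug or relapse₁₂".
- **Reinfected subjects are sequenced.** SAP 10.8 orders sequencing of a post-treatment sample with HCV RNA of at least 1000 IU/mL in non-responders without virologic failure. The reasons it names include "HCV reinfection, missing SVR₁₂ data or other reasons as described in Section 10.1".
- **The definition.** "Treatment-emergent substitution: A post-baseline substitution or an enriched polymorphism". A post-baseline substitution is below 2% at baseline and at 2% or more later. An enriched polymorphism has risen by at least 20 percentage points. Neither requires the two samples to come from the same virus.
- **The comparators.** The first Analysis 4 listing uses the subject's own baseline: "Listings by subject of all treatment-emergent substitutions relative to the baseline amino acid sequences will be provided for each DAA target". The second covers signature positions only and compares with a reference sequence, which SAP 10.8 requires to be subtype-specific.
- **Protocol 8.1.4** has the same Analysis 4 population, and there both listings compare with baseline.
- **Protocol 3.0** reports that one GT3 subject in the registrational programme was "determined to have been reinfected with GT3a virus distinct from the one present at baseline". Substitutions were then analysed in 22 subjects, not 23.

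**The concern.** A substitution relative to baseline is informative only if the later virus descends from the baseline virus. After relapse it does. After reinfection it does not: SAP 10.1 defines reinfection by a switch of genotype, subtype or clade. Residues that the new virus carries naturally and the old one lacked then meet the definition of treatment-emergent.

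The first listing is not limited to signature positions, so a strain switch could add many entries. Post-baseline substitutions in subjects without SVR12 are a named resistance variable (protocol 5.3.3.3). What is at stake is whether a reader of that listing takes a new strain's natural variation for variation selected by the drug.

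**Working it through.** The point rests mainly on definitions, so the first step follows one subject through the rules. The arithmetic after it gives the size.

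**1. A reinfected subject traced through the SAP**

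| Step | Rule | Result |
|---|---|---|
| Reason for non-response | 10.1: reinfection takes precedence over relapse and premature discontinuation | SVR12 non-responder, category reinfection |
| Secondary endpoint | 10.1 and 10.4: reinfection is excluded from Relapse12 | Not a relapse |
| Sequencing | 10.8: reinfection is named; sample of at least 1000 IU/mL | Post-treatment sequence exists |
| Analysis 4 population | 10.8: no SVR12, post-baseline data available | Included |
| First listing | 10.8: below 2% at baseline, at least 2% later | Differences from the old virus listed as treatment-emergent |
| Second listing | 10.8: relative to reference | Baseline not used |

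The SAP separates reinfection from relapse for the secondary endpoint but not for the first Analysis 4 listing. Subjects reinfected after achieving SVR12, or without a sample of at least 1000 IU/mL, are not affected.

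**2. The programme's count (protocol 3.0)**

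- Virologic failures: 2 (GT1) + 2 (GT2) + 19 (GT3) = 23.
- Less one reinfected GT3 subject: 23 − 1 = 22, and 19 − 1 = 18 in GT3.
- The stated proportions use 18: 11/18 = 61.1% and 16/18 = 88.9%.

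The reinfected subject was therefore left out of that substitution analysis.

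**3. Expected non-responders in this trial**

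Inputs: 100 subjects and an SVR12 rate of 97% (SAP 4.3; protocol 8.2). Expected non-responders = 100 × (1 − 0.97) = 3, from any cause. Those without a sample of at least 1000 IU/mL contribute nothing to Analysis 4.

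**4. Chance of at least one reinfection**

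The documents give no reinfection rate for this trial. With rate r, the expected number is 100r and the chance of at least one case is 1 − (1 − r)^100.

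| Rate r | Source | Expected cases | Chance of at least one |
|---|---|---|---|
| 1/2256 | One case over the TN + TE-PRS total in protocol Table 2 | 0.04 | 4.3% |
| 0.5% | Assumption | 0.5 | 39% |
| 1% | Assumption | 1.0 | 63% |
| 2% | Assumption | 2.0 | 87% |

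The first row assumes that the single reported case was the only one in that set and that its rate carries over. The other rows only show how the answer moves.

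**5. Weight of one case**

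If a reinfection did occur among 3 non-responders, it would be 1/3 of them. That share is conditional on the event in step 4.

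**The case against.** The strongest reply is that nothing is counted or tested. Analysis 4 produces by-subject listings. The analyses that give percentages or Fisher tests (Analyses 1 to 3) use baseline polymorphisms. SAP 10.3 and 10.7 also require listings of non-responders by reason, so a careful reader could identify a reinfected subject. This stands, and it limits the consequence to a wrong label. It does not remove the fault, because Analysis 4 itself carries no flag.

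Several stronger readings are tempting, and the documents do not support them:

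- **All of Analysis 4 is invalid for these subjects.** In the SAP the second listing compares with a reference and does not use the treatment-emergent label. It is sound and should stay.
- **Reinfected subjects should not be sequenced.** SAP 10.1 identifies reinfection primarily by phylogenetic analysis, which needs the sequence.
- **The plan will report a false resistance rate.** No rate, interval or test uses the label.
- **One third of the Analysis 4 subjects will be invalid.** That presumes a reinfection among about 3 non-responders. The documents' only base rate makes any case unlikely.
- **Injection drug use makes reinfection likely here.** It is a planned baseline and subgroup category, but exclusion criterion 5 removes recent drug abuse that the investigator judges makes a subject unsuitable. No reinfection rate is given for such subjects.

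The comparison with the registrational programme also has a limit. Protocol 3.0 describes an integrated analysis, and it does not show whether the individual studies' listings contained the reinfected subject. It does show that the sponsor took reinfection as a reason to leave a subject out of this comparison.

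Finally, protocols 5.3.3.3 and 8.1.4 define the population as non-SVR12 subjects without exception, so an exclusion departs from the protocol. That is correct and has to be documented.

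**Conclusion.** The point holds, and it is minor. Followed as written, the first Analysis 4 listing in SAP 10.8 would label differences between two separate viruses as treatment-emergent for any SVR12 non-responder classed as reinfection with a post-treatment sample of at least 1000 IU/mL. This follows from stated rules, not from missing detail.

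No primary, secondary or safety result changes. Few subjects, possibly none, will be involved: about a 4% chance of any case among 100 at one case per 2256, and more only under rates that the documents do not supply. With about 3 non-responders expected at 97%, a single case could still supply many of the entries. The conclusion assumes only that the listing is programmed as the text reads.

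**What to change.** 1. In SAP 10.8, Analysis 4, add a sentence excluding subjects in the HCV reinfection category from the listing of treatment-emergent substitutions relative to baseline.
2. Keep these subjects sequenced. Keep them in the second listing, relative to the subtype-specific reference for the post-treatment virus, with a reinfection flag.
3. Apply the same exclusion to the baseline-relative Analysis 4 listings of protocol 8.1.4 at an amendment, or record the difference in SAP Section 12.1, which now lists only the removal of HIV co-infection analyses.

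The cost is one sentence, one filter and one flag, using a category that SAP 10.1 already defines, plus the protocol change or the Section 12.1 entry. No new data are needed.
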